4.4.3 The Per Protocol (PP) Population

The per-protocol (PP) population will include all subjects of the full analysis set who fulfill all of the following conditions:

- Provide valid, i.e., non-missing haemostatic efficacy data.
- Provide a 1-hour post-infusion MCF value.
- Received $\geq 90\%$ of the planned total dose of the IMP in the first infusion.
- Received $\geq 80\%$ of the calculated dose (no dose was calculated, 0% will be assumed) of the IMP over all further infusions according to the treatment schedule
- Did not meet any of the following exclusion criteria:
 - Bleeding disorder other than congenital fibrinogen deficiency.
 - End-stage liver disease (i.e., Child-Pugh-score B or C).
 - Suspicion of an anti-fibrinogen inhibitor as indicated by previous IVR, if available < 0.5 (mg/dL)/(mg/kg).
 - Treatment with any fibrinogen concentrate or other fibrinogen-containing blood product within 2 weeks prior to start of treatment for the bleeding episode or surgery.
- Did not use any coagulation-active drug (i.e., non-steroidal anti-inflammatory drugs, warfarin, coumarin derivatives, platelet aggregation inhibitors) within 1 week prior to start of treatment for the bleeding episode or surgery, or as a planned or expected medication during the time period from Day 1 until 24 hours (i.e., 1 day) after the last Octafibrin infusion.
- Surgical procedure with a need for at least one infusion of the IMP with an overall clinical assessment of haemostatic efficacy.

FORMA-02	JSS Medical Research - Data Management		
Statistical Analysis Plan			
Form Number: MNI-DM-BIS-01 v 6.0-T1	Current Version Number: 2.0	Previous Version Number: 1.1 9-April-2015	Date:11-July-2016

Any protocol deviations other than those with respect to the above conditions for the PP population must be agreed upon in writing by the Sponsor and the study statistician, and in any case, before database closure.

The efficacy analysis will be performed for bleeding events using the full analysis set (ITT analysis) and for the PP population (PP analysis). An additional analysis will also be performed for the surgical population.

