4.3 Study Duration

4.3.1 Planned Duration for an Individual Subject

For subjects receiving on-demand treatment.

- the individual **subject observation and follow-up period** for each documented episode starts with the first dose of Octafibrin administered for on-demand treatment of an acute bleeding episode (Day 1) and will be followed for up to Day 30.
- Each subject's **treatment observation period** is defined according to the severity of the event and will last at least 3 days for minor and 7 days for major bleeding episodes.

For subjects undergoing surgical prophylaxis.

- the **surgical observation period** starts with the first dose of Octafibrin administered prior to elective surgery (Day 1) and, depending on the severity of the event, will last at least 3 post-operative days for minor and 7 post-operative days for major surgeries or until the day of the last post-operative infusion, whichever comes last.

During the study observation period, enrolled patients will be treated for any bleeding episodes or planned surgeries that can be managed under the protocol. Patients may remain in the study until the 24th patient has at least one documented bleeding episode.

As many bleeding episodes or surgeries as possible occurring throughout the study observation period will be documented. Only the first bleeding episodes will be used for the analysis of the primary endpoint (see Section 3.2.1). All bleeding episodes documented in the study will be assessed as a secondary endpoint (see Section 3.2.2).

Patients who were screened for the study but do not present with a bleeding episode or planned surgery during the study observation period will be considered 'no treatment' patients.

The individual observation period by subject starts with the first dose of Octafibrin administered for on-demand treatment of an acute bleeding episode or prior to elective surgery (Day 1). Subjects enrolled will be treated for any bleeding episodes or planned surgeries during the study observation period. They may remain in the study until the 24th subject has at least one documented bleeding episode.

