6.3 Handling of Drop-outs and Missing Values

In general, if not stated differently, missing data will not be imputed.

If the haemostatic efficacy assessment is missing it will be set to "none" in the ITT analysis. Subjects with missing haemostatic efficacy assessment will be excluded from the per-protocol PP population. LOCF (Last observation carried forward) approach will be used for body weight measurement for all analysis involving dose/kg BW.

Missing MCF and IVR values will not be replaced.

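### The per-protocol set for bleeding efficacy requires a 1-hour MCF value that the clinical rating does not use, and its conditions do not say which episode they apply to.

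*SAP*

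**What the plan says.** SAP 4.4.3 defines one PP population: FAS subjects who meet every condition on a list. Protocol 9.3.3 has essentially the same list. The conditions that matter here are:

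- Clinical outcome: "Provide valid, i.e., non-missing haemostatic efficacy data".
- Surrogate: "Provide a 1-hour post-infusion MCF value".
- Dose: at least 90% "of the planned total dose of the IMP in the first infusion", and at least 80% of the calculated dose "of the IMP over all further infusions according to the treatment schedule".
- Prior products: no "Treatment with any fibrinogen concentrate or other fibrinogen-containing blood product within 2 weeks prior to start of treatment for the bleeding episode or surgery". The bullet on coagulation-active drugs uses the same reference to the bleed or surgery.
- Surgery: a final bullet describes a surgical procedure that needs study drug and has an overall efficacy assessment.

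SAP 4.4.3 then says that bleeding efficacy is analysed in both the FAS and the PP set. Its closing clause on written agreement by the sponsor and statistician covers only deviations other than those listed.

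SAP 6.3 adds: "Missing MCF and IVR values will not be replaced". SAP 4.3.1 fixes the unit of the primary analysis: "Only the first bleeding episodes will be used for the analysis of the primary endpoint". The FAS in SAP 4.4.2 has no MCF condition.

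**The concern.** The rating in SAP 3.2.1 rests on cessation of bleeding, other haemostatic intervention and fall in haemoglobin. MCF does not enter it. Protocol 7.2.2.1 has MCF assessed from frozen citrated plasma, with data going to a central laboratory, and SAP 3.2.2 lists it as a secondary endpoint. Its absence says nothing about adherence or about whether the clinical outcome can be evaluated.

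The second difficulty is the unit. The primary endpoint belongs to one episode, whereas PP membership belongs to the subject. Subjects may have several bleeds and surgeries in a study planned to run for up to 5 years, and no condition says which of these counts.

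At stake is how the PP result can be read. With 24 subjects, losing or admitting one or a few for reasons unconnected with the first bleed can move the PP lower limit across the threshold. An open-label study should not leave such membership questions to be settled once ratings are known.

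**Working it through.** **Inputs from the SAP.** N = 24 (6.1.1). From 8.2: threshold 0.6, two-sided 95% Blyth-Still-Casella interval, assumed true success rate 0.95. The supplied Protocol 6.0 uses 0.7 and 90%. The SAP figures are used here because SAP section 1 says that it supersedes the protocol's statistical sections.

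**The plan's own figures.** The chance of at least r successes in 24 at p = 0.95 is the sum over k ≥ r of C(24,k)·0.95^k·0.05^(24−k). For r = 19, 20, 21 and 22 this gives 0.999, 0.994, 0.970 and 0.884, matching SAP Table 1. Recomputed lower limits are 0.594, 0.634, 0.692 and 0.744, within 0.001 of the table. The passing rule at n = 24 is therefore at least 20 successes.

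**Loss from the MCF bullet.** The documents give no missing-MCF rate, so 5–10% of subjects is an assumption.

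- Expected PP size = 24 × (1 − q): 24 × 0.95 = 22.8 and 24 × 0.90 = 21.6.
- Chance of losing at least one subject, if losses are independent = 1 − (1 − q)^24: 0.71 and 0.92.

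**Effect on individual results.**

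| FAS result | Lower limit | Subjects without MCF | PP result | Lower limit |
|---|---|---|---|---|
| 20/24 | 0.634, passes | four successes | 16/20 | 0.589, fails |
| 19/24 | 0.594, fails | one failure | 19/23 | 0.615, passes |

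**Effect on average.** If values are missing at random, the overall chance of passing hardly moves. At n = 22 the rule is at least 18 (lower limit 0.611), and at n = 21 at least 17 (0.602). Both still allow four failures, as n = 24 does. At p = 0.95 the chances of passing are 0.996 and 0.997, against 0.994 at n = 24. At n = 20 only three failures are allowed (at least 17), and the chance is 0.984.

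**Which episode.** Two readings can be set side by side.

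- *Over the whole study.* The wording "within 2 weeks prior to start of treatment for the bleeding episode or surgery" could refer to any treated event, and "of the IMP over all further infusions according to the treatment schedule" could cover all infusions in the study. A deviation at a later event would then remove a valid first-bleed rating. But the MCF bullet asks for only one value, and SAP 3.2.2 schedules 1-hour samples after the first and last infusion of each bleed. A value from a later bleed would then keep in a subject whose first bleed had none.
- *Within one episode.* The bullets use the singular, and Protocol 6.1.2.1 and 6.1.2.5 restart Day 1 for each bleed. On this reading only first-bleed events count for the primary analysis, and a missing first-bleed MCF value excludes.

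The text does not choose between them.

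**Surgical bullet.** Because every condition must be met, a subject who bled but had no surgery fails the list as written. A subject who had only surgery fails the MCF bullet, because the flow chart in SAP 4.5.2 schedules no MCF sample. Read literally, the set holds only subjects with both.

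**The case against.** The strongest reply is that little is at risk. The FAS keeps every affected subject. SAP 8.1 and 6.3 set a missing clinical rating to the worst category, which is the rule of an FAS-based primary analysis. At the assumed rates the PP set loses one or two subjects and, under random loss, passes about as often as before. All of this stands. It limits the point to the PP analysis and to borderline results. Neither set is explicitly named as primary, however, so the PP result cannot be dismissed by reference to the text.

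A second reply is that the singular wording and the per-episode Day 1 make an episode-specific reading at least as natural. That is fair. The later-episode problem is an ambiguity, not a demonstrated loss of data. It does not remove the MCF condition, which excludes subjects on either reading if no qualifying value exists.

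Three stronger claims might be inferred, and the documents do not support them:

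- **That a fifth to a third of subjects would be lost.** Assuming a 5–10% breach rate at each of four independent episodes, 1 − (1 − q)^4 gives 19–34%. Neither the rate nor four episodes per subject is in the documents, and Protocol 3.3 expects wide variation in bleeds per patient. The formula is also wrong for MCF. If one value from any bleed is enough, the chance of having none is q^4, about 0.000006 to 0.0001.
- **That frequent bleeders are removed preferentially.** For MCF under the whole-study reading, more bleeds make exclusion less likely.
- **That PP is the designated check on the primary result.** SAP 4.4.3 says only that both sets are analysed.

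**Conclusion.** The point holds as a defect in how the PP set is specified. As written, a missing MCF value removes an adherent subject with a valid first-bleed rating, and the written-agreement clause cannot restore them. The missing episode reference can wrongly exclude or wrongly admit. The surgical bullet cannot sensibly stand in a list where every condition must be met.

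The size is modest: about one to two subjects of 24 if 5–10% lack a value, which is an assumed range. The example reversals show what can happen in borderline results, not what is likely. They also require the missing values to fall on particular subjects. Dose and drug-use deviations within the first bleed are ordinary PP exclusions and are not disputed. The change should be made, but the FAS result does not depend on it.

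**What to change.** In SAP 4.4.3, and correspondingly in Protocol 9.3.3:

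1. Delete the MCF bullet from the PP set for bleeding. Use MCF availability only to define an MCF-evaluable subset for the analyses in SAP 8.3.1, naming the infusion and episode that the value must come from.
2. State that the remaining bleeding-related conditions apply to the first documented bleed for the primary PP analysis, and to each episode separately for the all-bleeds analysis in SAP 8.3.4.
3. Move the surgical-procedure bullet to the definition of the surgical population in SAP 4.4.4.

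The cost is a wording change and an episode-level flag in programming, with no new data or subjects. The efficacy and MCF tables will have different denominators, which a footnote should explain. The change should be made before database closure, and preferably before first-bleed ratings are reviewed.

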3.2 Overall Study Design and Plan

This is a multinational, multi-centre, prospective, open-label, uncontrolled, Phase III study to assess the efficacy and safety of *Octafibrin* for on-demand treatment of acute bleeding and surgical prophylaxis in subjects with congenital fibrinogen deficiency.

A total of 24 male and female subjects with congenital fibrinogen deficiency will be enrolled in the study. This will include at least 4 subjects aged between 12 and 18 years (only 18 and above in Russia). This will also include at least 4 surgeries, 2 of which should be performed in subjects aged between 12 and 18 years (only 18 and above in Russia). The study will be conducted in approximately 15 study centres worldwide.

During the study observation period, enrolled patients will be treated for any bleeding episodes or planned surgeries that can be managed under the protocol. Patients may remain in the study until the 24th patient has at least one documented bleeding episode. The study will be considered completed when a minimum of 24 subjects have at least one documented bleeding episode. The study as a whole should be completed within 5 years.

As many bleeding episodes or surgeries as possible occurring throughout the study observation period will be documented. Only the first bleeding episodes will be used for the analysis of the primary endpoint. All bleeding episodes documented in the study will be assessed as a secondary endpoint.

The investigator will inform the monitor of any recruitment difficulty or delay of the anticipated completion date.

Patients should be treated with the investigational medicinal product (IMP) whenever possible. If, in the opinion of the investigator, a bleeding episode is not effectively stopped or surgical prophylaxis is not adequate after the recommended dose of *Octafibrin* has been administered, the subject may receive a different licensed fibrinogen concentrate (e.g., Haemocomplettan P®/RiaSTAPTM) or whatever the investigator considers standard of care. The use of another licensed fibrinogen concentrate is also permitted in emergency situations, e.g., if the IMP is not available for the patient in time.

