8 EFFICACY ANALYSIS

8.1 Primary Efficacy Analysis

For bleeding efficacy, the primary endpoint is the overall clinical assessment of the haemostatic efficacy of Octafibrin in treating the first documented bleeding episode of each patient.

The first bleeding episode covers the time period from the first Octafibrin infusion until 24 hours (i.e., 1 day) after the last infusion or the end of the treatment observation period, whichever comes last. Frequency distribution will be provided for the haemostatic efficacy scale data. In addition, a 95% CI for the success rate in haemostatic efficacy (excellent or good) according to Casella (Blyth-Still-Casella interval) will be computed using StatXact® software.

For the following subjects the haemostatic efficacy outcome will be set to the worst category i.e., "none":

- Subjects who withdraw from the study due to lack of efficacy.
- Subjects receiving cryoprecipitate, or concentrates containing fibrinogen other than the IMP between first infusion and efficacy assessment (unless it is clearly documented that these products were administered for reasons unrelated to efficacy [e.g., pharmacy error]).
- Subjects with missing haemostatic efficacy assessment.

Haemostatic efficacy will be displayed by co variables (sex, age groups, race, weight and type of bleeding) in tables or with co variables in listings depending on the number per subgroup.

FORMA-02	JSS Medical Research - Data Management		
Statistical Analysis Plan			
Form Number: MNI-DM-BIS-01 v 6.0-T1	Current Version Number: 2.0	Previous Version Number: 1.1 9-April-2015	Date: 11-July-2016

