8.2 Hypothesis Testing and Determination of Sample Size

The following hypothesis will be tested:

$$H_0: p \leq 0.6$$

Against the alternative

$$H_A: p > 0.6$$

Where p is the proportion of subjects with successful haemostatic efficacy (i.e.; 'excellent' or 'good').

The null hypothesis will be tested against the alternative by comparing the lower limit of the two-sided 95% Blyth-Still-Casella confidence interval for the proportion of patients with successful haemostatic efficacy with the predefined threshold of 0.6.

Due to practical limitations in subject enrolment and total study duration due to the very small number of patients with this indication, no real sample size calculation was performed on basis of statistical power considerations. Instead, the probabilities and associated confidence intervals (CIs) for different outcomes are provided, assuming a true success rate of 0.95.

Assuming that the study treatment is successful (i.e. the haemostatic efficacy assessment is 'excellent' or 'good') in 95% of the subjects, the success rates given in Table 1 will be observed in the 24 study subjects with the following probabilities:

Table 1: Overall clinical assessment of haemostatic efficacy

Outcome (n/N)	Percentage	Probability for the outcome (binomial)	95% (2-sided) confidence interval ^a
≥19/24	≥79.1%	0.999	0.594–0.914
≥20/24	≥83.3%	0.994	0.633–0.941
≥21/24	≥87.5%	0.970	0.691–0.965
≥22/24	≥91.7%	0.884	0.744–0.985

n = number of subjects with 'excellent' and 'good' haemostatic efficacy; N = total number of subjects.

^a Blyth-Still-Casella interval, realised by StatXact® software.

Hence, assuming that treatment with Octafibrin is associated with a true success rate of 95% of the 24 subjects, there will be a 99.4% probability that at least 20 of 24 subjects will have a successful assessment. In case of 20 successful assessments, the lower boundary of the 95% CI will be 0.633, i.e., > 60%.

FORMA-02	JSS Medical Research - Data Management	 <small>RESPONSIVE RELIABLE RESULTS</small>	
Statistical Analysis Plan			
Form Number: MNI-DM-BIS-01 v 6.0-T1	Current Version Number: 2.0	Previous Version Number: 1.1 9-April-2015	Date: 11-July-2016

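### The per-protocol rules in SAP 4.4.3 and 6.3 can drop subjects because Octafibrin failed, and no sentence says that the full analysis set carries the test

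*SAP*

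**What the plan says.** **Failure rule.** SAP 8.1 sets the outcome to *none* for three groups: "Subjects who withdraw from the study due to lack of efficacy"; subjects given cryoprecipitate or another fibrinogen concentrate between first infusion and assessment, unless clearly documented as unrelated to efficacy; and subjects with no rating. Protocol 9.4.1 has the same rule.

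**PP conditions.** SAP 4.4.3 (and Protocol 9.3.3) requires, among other things, a non-missing rating, at least 90% of the planned first dose, and at least 80% "of the calculated dose (no dose was calculated, 0% will be assumed) of the IMP over all further infusions according to the treatment schedule". SAP 6.3 sets a missing rating to *none* in the ITT analysis, but for PP it says: "Subjects with missing haemostatic efficacy assessment will be excluded from the per-protocol PP population".

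**Switching.** Protocol 3.2 provides that, if a bleed is not effectively stopped after the recommended Octafibrin dose, "the subject may receive a different licensed fibrinogen concentrate".

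**Analyses.** SAP 4.4.3 runs the bleeding efficacy analysis on both the FAS and PP. The test in SAP 8.2 compares the lower limit of the "two-sided 95% Blyth-Still-Casella confidence interval for the proportion of patients with successful haemostatic efficacy with the predefined threshold of 0.6". Neither section says which set decides it.

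**The concern.** A PP set is meant to remove subjects who did not follow the plan. Here two of its conditions can be failed because the product did not work.

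- **Missing rating.** Protocol 6.1.2.3 places the final rating 24 hours after the last infusion or at the end of the treatment observation period, whichever is later. Protocol 6.1.2.2 makes that period at least 3 days (minor bleeds) or 7 days (major bleeds). A subject who withdraws earlier for lack of efficacy may have no rating: *none* in the FAS, absent from PP.
- **Dose shortfall.** After a switch to another product, a further Octafibrin dose may be calculated but withheld. Or the other product may raise the measured level, so that no dose is calculated and 0% is assumed. Either way the 80% condition can fail.

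With 24 subjects, removing one or two failures can change whether the PP limit clears 0.6. A PP result above the threshold could then be read as confirming the FAS when it partly reflects who was left out.

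**Working it through.** **Inputs from the documents.** From SAP 8.2: the threshold 0.6, the two-sided 95% Blyth-Still-Casella interval, a calculation "assuming a true success rate of 0.95", and 24 subjects. Protocol 9.1 (version 6.0) uses 0.7, a 90% interval and 90% success. SAP section 1 says that it supersedes the protocol's statistical sections, so the SAP values are used.

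**Assumptions.** The documents give neither q, the share of failures dropped from PP, nor s, the share of successes dropped. Ranges are shown.

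**1. The plan's own figures reproduce.** Binomial tails for 24 subjects at 0.95 and lower limits by a numerical Casella refinement:

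| Outcome | Tail, SAP | Tail, recomputed | Lower limit, SAP | Lower limit, recomputed |
|---|---|---|---|---|
| ≥19/24 | 0.999 | 0.9990 | 0.594 | 0.594 |
| ≥20/24 | 0.994 | 0.9940 | 0.633 | 0.634 |
| ≥21/24 | 0.970 | 0.9702 | 0.691 | 0.692 |
| ≥22/24 | 0.884 | 0.8841 | 0.744 | 0.745 |

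**2. Failures dropped, no successes dropped.** PP rate = p / [p + (1 − p)(1 − q)]. At p = 0.95:

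- q = 0.25: 0.95 / (0.95 + 0.0375) = 96.2%
- q = 0.50: 0.95 / (0.95 + 0.025) = 97.4%
- q = 0.75: 0.95 / (0.95 + 0.0125) = 98.7%

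The rise is 1.2 to 3.7 points. Expected failures number only 24 × 0.05 = 1.2.

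**3. Effect on the threshold.**

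| FAS count | FAS lower limit | Failures dropped | PP count | PP lower limit |
|---|---|---|---|---|
| 19/24 | 0.594 (fails) | 1 | 19/23 | 0.615 (passes) |
| 18/24 | 0.554 (fails) | 2 | 18/22 | 0.611 (passes) |

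At 95% true success, a FAS count of 19 or fewer has probability 1 − 0.994 = 0.006, so a reversal is unlikely if the SAP's assumption is right. It matters when the product does worse. At a true rate of 0.60, the chance that the PP limit exceeds 0.6 is 1.3% for q = 0, 8.7% for q = 0.25, 24.1% for q = 0.50 and 58.2% for q = 0.75. With 24 × 0.4 = 9.6 expected failures, the last three imply about 2.4, 4.8 and 7.2 subjects dropped, and no successes lost.

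**4. Successes dropped as well.** The 0% wording, read literally, also excludes a subject who needed only one infusion, a case foreseen in the note to Protocol 6.1.2.1. PP rate = p(1 − s) / [p(1 − s) + (1 − p)(1 − q)]. At p = 0.95 and q = 0.5:

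- s = 0: 97.4%
- s = 0.50: 0.475 / (0.475 + 0.025) = 95.0%
- s = 0.75: 0.2375 / (0.2375 + 0.025) = 90.5%

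The net shift can be up, nil or down.

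**The case against.** Four points can be made on the other side.

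- **Many failures stay.** Protocol 3.2 allows a switch for non-response only after the recommended dose has been given, so the first-dose condition can be met. A subject rescued after receiving every dose due, or with a recorded *moderate* or *none* and complete dosing, remains in PP as a failure. This stands, and q near 1 is not realistic.
- **The direction is not fixed.** A reader might infer that PP always overstates success. The documents do not support that, because the 0% wording that can exclude a switched subject can equally exclude a single-infusion success (step 4). If it is read so that single-infusion subjects stay in, the no-dose-calculated route weakens for switched subjects too. This also stands, but opposing exclusions do not make PP sound: both depend on how the bleed responded.
- **The missing-rating route is narrow.** It needs withdrawal for lack of efficacy and no rating. SAP 8.1 lists such withdrawal separately from a missing rating and does not limit the rule to the FAS, so the subject might be treated as having an assigned outcome. SAP 6.3 nevertheless excludes missing ratings without exception. The text supports both readings and should be settled.
- **The FAS protects the conclusion.** It keeps these subjects as *none*, Table 1 uses all 24, and SAP 8.2 counts a missing rating as failure, which has effect only if such subjects are in the set. This points to the FAS as the intended basis of the test, but no sentence says so.

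**Conclusion.** The PP rules can exclude subjects because of outcome rather than non-adherence, and the SAP has no safeguard against it. This mechanism alone raises the PP rate by 1.2 to 3.7 points at 95% true success for q = 0.25 to 0.75, and one dropped failure can carry the PP limit across 0.6. These sizes rest on assumed q and on no successes being lost.

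A reader might go further and infer that all failures leave PP, or that the trial's main result is biased. Neither follows: recorded failures with adequate dosing remain in PP, and the FAS result is unaffected. The defect lies in the PP analysis and in the SAP's silence on which set decides. It is worth correcting in the SAP, but it does not threaten the trial.

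**What to change.** Amend SAP 4.4.3 and 6.3 as follows.

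- **(a)** State that the FAS analysis carries the hypothesis test in 8.2 and that PP is supportive.
- **(b)** Assess the PP dose conditions only on Octafibrin doses due before any switch to another fibrinogen product, stop or withdrawal for lack of efficacy. Treat the further-infusion condition as met when no further infusion was required.
- **(c)** Keep in PP, as failures, subjects set to *none* under 8.1 because of lack of efficacy, whether or not a final rating exists. Put the same exception in 6.3.

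The cost is SAP wording only. No new data are needed and no dosing or clinical rule changes. The PP success rate may come out slightly lower than without (c).
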